13.5. Secondary Endpoint: Incidence of FACEs by Category

Incidence of cardiac, cerebrovascular, and renal clinical events separately by each specific category (including death in these categories) will be analysed as described in Section 13.2 for the composite FACEs.

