13.2. Secondary Endpoint: Prevalence of FACEs

Treatment Switch

The first analysis will address events that occur on therapy from the Analysis Start Date up until 30 days after the patient stops therapy or from the switch date to the date of a subsequent switch or stopping therapy. The second analysis will address events that occur on therapy from the Analysis Start Date up until the patient stops therapy or switches therapy or from the switch date to the date of a subsequent switch or stopping therapy.

Analysis Method

The prevalence of FACEs is calculated as a ratio of patients with at least one FACE on a given therapy divided by the number of patients on that therapy. If a patient starts dialysis or receives a kidney or heart transplant, the events afterwards will be excluded.

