13.3. Secondary Endpoint: Incidence of FACEs

As this is an observational study, patients may switch or stop therapies. If a patient starts dialysis or receives a kidney or heart transplant, the events afterwards will be excluded.

The analysis of the incidence rate (number of patients with at least 1 event per 1000 person-years) will be performed on the Primary and Secondary Effectiveness Populations.

Treatment Switch

The analysis will address events that occur on migalastat or ERT therapy from the Analysis Start Date or switch date up until 30 days after the patient stops therapy or switches therapy. For the patients untreated at enrollment to the study, the analysis will address events from the time of diagnosis until the patient starts a therapy or during periods that they are untreated after a switch.

The second analysis will address events that occur on migalastat or ERT therapy from the Analysis Start Date or switch date. For the patients untreated at enrollment to the study, the analysis will address events from the time of diagnosis until the patient starts a therapy or during periods that they are untreated after a switch.

Analysis Methods

The calculation of the incidence rate (number of events per 1000 person-years) will be performed on the Primary and Secondary Effectiveness Populations.

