13.6. Secondary Endpoint: Prevalence of FACEs by Category

Prevalence of cardiac, cerebrovascular, and renal clinical events separately by each specific category (including death in these categories) will be analysed as in Section 13.3 for the composite FACEs.

13.7. Secondary Endpoint: Estimated Glomerular Filtration Rate to Compare Migalastat-treated, ERT Treated, and Untreated Patients

Estimated GFR will be summarized using descriptive statistics by treatment at diagnosis date. Descriptive statistics will be displayed for change from Analysis Start Date (time of diagnosis or treatment start) to e.g. time points such as the date of the first treatment switch, date of the treatment to migalastat or any other time points of interest.

For dialysis and transplant patients, the Analysis Start Date for eGFR will be reset to the last value before dialysis start or before transplantation and used thereafter.

Analysis Methods

Data will be listed. Listings will contain flags indicating therapy change. Spaghetti plots will indicate what treatment group a patient was on at the time of measurement.

Longitudinal analysis using Mixed Model for Repeated Measures (MMRM) will be used to analyze data over time. Trends over time using adjusted means will be plotted. Missing post-Analysis Start Date measurements will not be imputed as MMRM method allows for missing values. This analysis only accounts for changes over time regardless of therapy.

Covariates are:

- sex
- enrollment age as a continuous variable
- enrollment eGFR as a continuous variable
- proteinuria based on the UPCR value at enrollment
- LVMi at enrollment
- history of cardiac, cerebrovascular, and renal clinical events (a binary endpoint based on the composite event) prior to enrollment
- length of treatment for Fabry disease

If the measurements are not available, measurements prior to and closest to the Analysis Start Date will be used. In case that more than 50% of values are missing for a given covariate, it will be dropped from the analysis.

Additionally, the annualized rate of eGFR change will be calculated as the slope of the individual patients' regression equations over time. The annualized rate of change will be analyzed using t-test for migalastat-treated versus untreated patients. This analysis only accounts for changes over time regardless of therapy.

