15.9. Electrocardiogram

Echocardiograms will be analyzed in the same way as clinical laboratory tests (Section 15.6).

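### SAP 13.5 and 13.6 exchange the method references for category incidence and category prevalence, and 13.3 leaves its incidence numerator unsettled: a limited correction to secondary summaries

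*SAP*

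**What the plan says.** SAP 3.2 lists incidence and occurrence of cardiac, cerebrovascular and renal events, each by category, as secondary endpoints. Their methods in 13.5 and 13.6 are given by reference only.

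- SAP 13.5, incidence by category: "will be analysed as described in Section 13.2 for the composite FACEs".
- SAP 13.6, prevalence by category: "will be analysed as in Section 13.3 for the composite FACEs".

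The two targets are:

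- SAP 13.2 is the prevalence section. Its estimator is a "ratio of patients with at least one FACE on a given therapy divided by the number of patients on that therapy".
- SAP 13.3 is the incidence section: "The analysis of the incidence rate (number of patients with at least 1 event per 1000 person-years) will be performed". Both effectiveness populations are covered. Its closing Analysis Methods paragraph gives a different numerator, the number of events.

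SAP 15.9, headed Electrocardiogram, contains one sentence: "Echocardiograms will be analyzed in the same way as clinical laboratory tests (Section 15.6". SAP 15.10, headed Echocardiogram, opens with the same sentence and adds the list of echo parameters. SAP 16.6 then treats the ECG analysis as already described.

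**The concern.** A programmer who follows 13.5 and 13.6 to the letter gives each category endpoint the other's estimator. The table headed category incidence would hold a percentage of patients and could not be read beside the composite incidence table, which holds a rate. Observation time per therapy can differ widely here. The Protocol has follow-up from 2001 and migalastat available from 2016, so it matters whether a statistic divides by person-time.

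The plan's own checks might not catch the slip. SAP 7.3 has outputs checked for consistency with the SAP, and a program that followed 13.5 literally would be consistent with it. SAP 17.1 declares no changes from the Protocol, so a proportion reported as incidence would be an undeclared departure.

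For ECG, a listed safety endpoint in both documents, the section that should give the method talks about a different test.

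**Working it through.** No stated figure in the plan depends on this point, so there is none to reproduce. The check is a trace of references, followed by an illustration on assumed values.

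**1. Trace each reference.**

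| Section | Quantity in its heading | Sent to | Estimator found there |
|---|---|---|---|
| SAP 13.5 | Category incidence | 13.2 | Patients with an event / patients on therapy |
| SAP 13.6 | Category prevalence | 13.3 | Per 1000 person-years |

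The SAP's contents list numbers 13.2 as prevalence and 13.3 as incidence, so text extraction does not explain the mismatch. SAP 13.4, category time to first event, correctly points to 13.1. SAP 13.8 and 13.9 refer to the methods by name and are unaffected.

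**2. Compare with the other definitions of incidence.** The Protocol's Secondary endpoints analysis expresses FACE incidence as events per 1000 patient-years. SAP 7.3 shows recurrent events for each specific FACE as a total count per 1000 person-years. Both disagree with 13.5 read literally and agree with 13.3.

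**3. Compare the treatment-switch windows.** In the first analysis of 13.3, the on-treatment window runs to 30 days after stopping or switching, whether the period began at the Analysis Start Date or at a switch. Untreated periods after a switch are counted explicitly. In the first analysis of 13.2, the 30 days attach to the period from the Analysis Start Date; a period that begins at a switch ends at the next switch or stop. The exchange therefore changes which events count as well as the denominator. The exclusion of events after dialysis or transplant is the same in both sections.

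**4. Check the numerator in 13.3.** The section states patients with at least one event per 1000 person-years, then number of events per 1000 person-years. These differ whenever a patient has more than one event. The Protocol uses events. Correcting the references alone would send 13.5 to an estimator that is still ambiguous.

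**5. Illustrate the relabelling (hypothetical values).** Take 40 patients, 320 person-years and 8 patients with a cardiac event.

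- Proportion: 8/40 = 20%.
- Rate: 8/320 × 1000 = 25 per 1000 person-years.

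Read literally, the plan prints 20% under incidence and 25 per 1000 under prevalence. Both numbers exist, in each other's place.

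**6. Illustrate why the label matters (assumed values).** Give two groups the same constant hazard h and follow-up t. The proportion is 1 − exp(−h·t); the rate stays at h.

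- h = 30 per 1000, t = 5 years: 1 − exp(−0.15) = 13.9%.
- h = 30 per 1000, t = 15 years: 1 − exp(−0.45) = 36.2%.
- Ratio of proportions: 36.2/13.9 = 2.6; rate ratio: 1.0.

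Over h from 10 to 50 per 1000 and follow-up pairs of 3/10, 5/15 and 6.5/20 years, the ratio of proportions runs from about 2.3 to 3.2, with the rate ratio at 1.0 throughout.

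**7. ECG.** Since 15.10 already covers echocardiograms, 15.9 most plausibly has one wrong word. With that word corrected, ECG takes the 15.6 method: counts of out-of-range and clinically significant results by treatment, with shift tables possible. SAP 9.2.1 gives interpretation categories for ECG, but under medical history collected at enrolment. The Protocol's variable tables show no ECG field.

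**The case against.** The strongest reply is that this is editorial and the intent can be recovered. The headings of 13.5 and 13.6 name the right quantities, and the Protocol and SAP 7.3 both put FACE incidence on a person-time basis. This stands, and it limits the severity. It does not remove the need to correct an operative instruction that says otherwise.

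Three stronger readings are tempting, and the documents do not support them.

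- *Category incidence rates would be lost.* They would not. The rate would still be produced under the prevalence heading, though with its own switch window.
- *The error would create a two- to three-fold spurious difference between treatments.* The ratios above rest on assumed hazards and follow-up. They describe any crude proportion, including the prevalence that 13.2 defines and that remains after the fix. They show what a wrong label could mislead a reader about, and do not measure the effect of the exchanged references.
- *ECG has no analysis and needs a new categorical one.* SAP 9.2.1 already summarises ECG results and overall interpretation, and a one-word correction to 15.9 brings in 15.6. The documents do not show that the interpretation categories were recorded after enrolment, so a prescribed shift-table analysis could require data that do not exist.

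**Conclusion.** The references in 13.5 and 13.6 are exchanged and wrong as written. If they are followed literally, the category incidence and prevalence endpoints each receive the other's estimator and switch window, and category incidence contradicts the Protocol and SAP 7.3. The unsettled numerator in 13.3 belongs to the same correction.

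The reach is limited to secondary summaries and, for 15.9, a safety summary. The primary composite analysis (13.1) and the category time-to-event analysis (13.4) do not change. No numerical size can be given, because the documents contain no category-level event counts and no follow-up by therapy. The conclusion about the references needs no assumption. The harm depends on a programmer applying them literally.

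**What to change.** 1. In SAP 13.5, change the reference to Section 13.3. In SAP 13.6, change it to Section 13.2.
2. In SAP 13.3, state one numerator for the incidence endpoint. Number of events agrees with the Protocol and with the statement in 17.1 that nothing has changed from it. If the rate of patients with at least one event is also wanted, label it separately and say whether person-time ends at the first event.
3. In SAP 15.9, replace echocardiograms by electrocardiograms, so that the 15.6 method applies and 16.6 refers to something that exists. Use the 9.2.1 interpretation categories where they were recorded.

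Items 1 and 2 are text edits that need no new data and are best made before programming. Item 3 is one word; how much ECG tabulation follows depends on what the records contain.

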13.6. Secondary Endpoint: Prevalence of FACEs by Category

Prevalence of cardiac, cerebrovascular, and renal clinical events separately by each specific category (including death in these categories) will be analysed as in Section 13.3 for the composite FACEs.

13.7. Secondary Endpoint: Estimated Glomerular Filtration Rate to Compare Migalastat-treated, ERT Treated, and Untreated Patients

Estimated GFR will be summarized using descriptive statistics by treatment at diagnosis date. Descriptive statistics will be displayed for change from Analysis Start Date (time of diagnosis or treatment start) to e.g. time points such as the date of the first treatment switch, date of the treatment to migalastat or any other time points of interest.

For dialysis and transplant patients, the Analysis Start Date for eGFR will be reset to the last value before dialysis start or before transplantation and used thereafter.

Analysis Methods

Data will be listed. Listings will contain flags indicating therapy change. Spaghetti plots will indicate what treatment group a patient was on at the time of measurement.

Longitudinal analysis using Mixed Model for Repeated Measures (MMRM) will be used to analyze data over time. Trends over time using adjusted means will be plotted. Missing post-Analysis Start Date measurements will not be imputed as MMRM method allows for missing values. This analysis only accounts for changes over time regardless of therapy.

Covariates are:

- sex
- enrollment age as a continuous variable
- enrollment eGFR as a continuous variable
- proteinuria based on the UPCR value at enrollment
- LVMi at enrollment
- history of cardiac, cerebrovascular, and renal clinical events (a binary endpoint based on the composite event) prior to enrollment
- length of treatment for Fabry disease

If the measurements are not available, measurements prior to and closest to the Analysis Start Date will be used. In case that more than 50% of values are missing for a given covariate, it will be dropped from the analysis.

Additionally, the annualized rate of eGFR change will be calculated as the slope of the individual patients' regression equations over time. The annualized rate of change will be analyzed using t-test for migalastat-treated versus untreated patients. This analysis only accounts for changes over time regardless of therapy.

An alternative analysis will only utilize data from periods on migalastat treatment and separately on the ERT treatment, and untreated periods.

13.8. Secondary Endpoints: Prevalence and Incidence of Clinically Significant change in mGFR or eGFR

The prevalence and incidence of a clinically significant change in mGFR and/or eGFR (according to KDIGO guidelines rapid progression is defined as a sustained decline in eGFR of more than 5 ml/min/1.73 m² /yr) from each baseline (diagnosis and start of treatment) to compare between migalastat-treated, ERT-treated patients and untreated patients will be analyzed using same methodology as for incidence and prevalence of FACEs.

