6.2. Missing Assessments

All data will be listed as collected. Descriptive statistics will be calculated on the data collected without replacement. For time to event, analysis data will be censored.

Missing and partial dates will be replaced as described in Section [6.1](#).

While it is possible that some patients will have missing or partial date information for SAEs or other safety data collections, analyses of the safety endpoints will include all patients in the Safety Population, unless specifically stated otherwise.

Missing data might be present for the analyses of the clinical laboratories and vital signs (eg, where the parameter was not measured at a required time points, which are the dates of treatment switch), and PROs. In many situations, there will often be other measurements of the parameter within a time frame that is applicable eg. during each treatment period. In such cases, the closest measurement to the switch time point within the treatment period will be used for analysis (Section 11). If such a measurement does not exist, then the patient will be excluded from the analysis of that variable at that timepoint. If 2 measurements are equidistant from the scheduled time point, the first one will be used.

Estimated GFR and LVMi data will be used as is and the actual time of the measurement will be utilized in the analysis. Analysis of LVMi will be exploratory.

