15.6. Clinical Laboratory Tests

Analyses of clinical laboratory assessments will focus on serum creatinine, urine protein, urine albumin, and urine ACR. Other labs results will be provided in by-patient listings. Analysis will be done using the same methodology as for eGFR (Section 13.7).

Data will be summarized using descriptive statistics will be displayed for change from Analysis Start Date (time of diagnosis or treatment start) to e.g. time points such as the date of the first treatment switch, date of the treatment to migalastat or any other time points of interest.

Analysis Methods

Data will be listed. Listings will contain flags indicating therapy change. Spaghetti plots will indicate what treatment group a patient was on at the time of measurement.

In the Safety Population, data will be analyzed from the time of diagnosis.

For dialysis and transplant patients, the Analysis Start Date creatinine (as it is done for eGFR in Section 13.7) will be reset to the last value before dialysis start or before transplantation and used thereafter.

All laboratory data, values, units, normal reference range, and out-of-range flags collected in the clinical database will be included in by-patient listings for further medical review.

The analysis will address data based on the actual exposure. The count of out of range values as well as counts of clinically significant results will be presented by treatment.

Summaries of out of range values and shift tables (using Analysis Start Date as baseline) could be prepared for timepoints of interest such as e.g. start of migalastat therapy. .

An additional table showing if a test result was out of range at any measurement over time will be prepared. A similar table will be prepared for potentially clinically significant values.

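### SAP 13.7 and 15.6 keep eGFR and creatinine recorded after dialysis or transplantation, against a reset baseline, which understates decline in the affected patients

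*SAP*

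**What the plan says.** SAP 13.7 describes eGFR by change from the Analysis Start Date (diagnosis or treatment start), by an MMRM, and by an annualized rate. For dialysis and transplant patients it adds that the Analysis Start Date for eGFR "will be reset to the last value before dialysis start or before transplantation and used thereafter". SAP 15.6 repeats the rule for creatinine: "the Analysis Start Date creatinine (as it is done for eGFR in Section 13.7) will be reset to the last value before dialysis start".

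The other relevant statements are:

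- **Which values enter (SAP 6.2):** "Estimated GFR and LVMi data will be used as is and the actual time of the measurement will be utilized in the analysis".
- **Slope (SAP 13.7):** "the annualized rate of eGFR change will be calculated as the slope of the individual patients' regression equations over time". No end date is set.
- **Test (SAP 13.7):** "The annualized rate of change will be analyzed using t-test for migalastat-treated versus untreated patients". SAP 3.2 sets the level at two-sided 0.05 without adjustment for multiple comparisons.
- **MMRM baseline covariate (SAP 13.7):** "enrollment eGFR as a continuous variable", not the reset value.
- **FACE analyses:** 13.1.1 censors at dialysis and at kidney or heart transplant. For prevalence, 13.2 says "If a patient starts dialysis or receives a kidney or heart transplant, the events afterwards will be excluded", and 13.3 has the same rule for incidence. Sections 13.8 (clinically significant GFR change) and 13.9 (albuminuria) adopt the FACE incidence and prevalence methods by reference.

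**The concern.** After transplantation, creatinine reflects the graft. On dialysis, it reflects clearance by the machine as well. Neither measures the course of the patient's own kidneys, which is what an annualized eGFR change is meant to describe. The patients concerned are those whose kidneys failed, so the contaminated records belong to the fastest decliners.

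The reset sentence adds an ambiguity, because it resets a date to a value. One programmer could compare later measurements with a new baseline, and another could carry the last value forward. A third could use the old baseline up to the event and the new one only after it. The SAP does not say whether or how the reset enters the MMRM or the slope.

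Annualized eGFR change is a named secondary endpoint with a formal test. About 115 patients are divided among three treatment groups and followed for more than 20 years. Groups may therefore be small, and long series after a transplant are possible.

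**Working it through.** **Is there a stop rule?** The documents give no planned slope, SD or count of dialysis or transplant patients, so there is no figure to reproduce. The first step is to compare the rules.

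| Analysis | Rule after dialysis or transplant |
|---|---|
| Time to first FACE, 13.1.1 | Censored |
| FACE prevalence and incidence, 13.2 and 13.3 | Later events excluded |
| GFR change and albuminuria endpoints, 13.8 and 13.9 | Inherit the FACE methods |
| eGFR change, MMRM and slope, 13.7 | Baseline reset; no exclusion |
| Creatinine, 15.6 | Baseline reset; no exclusion |

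The alternative eGFR analysis at the end of 13.7 splits data by therapy period, not by dialysis or transplant, so it does not close the gap.

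**Size within one patient (all values assumed).** Annual visits; native eGFR falls linearly from 60 to 12 over years 0 to 8. Then 2 or 8 annual values follow, which are a graft starting at 55 or 30 and losing 1 per year, or the value 12 carried forward. The slope is least squares, b = Sxy/Sxx, with Sxy = Σ(t - t̄)(y - ȳ) and Sxx = Σ(t - t̄)².

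Native record only: -360/60 = -6.0 per year.

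| Later values | Whole record, 2 values | Whole record, 8 values |
|---|---|---|
| Graft from 55 | -194/110 = -1.8 | 156/408 = +0.4 |
| Graft from 30 | -419/110 = -3.8 | -744/408 = -1.8 |
| 12 carried forward | -576/110 = -5.2 | -1224/408 = -3.0 |

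These whole-record slopes use no reset. They show the effect of missing truncation alone.

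**Effect of the reset itself.** The native change is 12 - 60 = -48. Measured from the reset value of 12:

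- Eight graft values from 55 to 48 give changes of +43 to +36, and a slope of 116/60 = +1.9 per year (years 8 to 16).
- A carried value gives a change of 0 and a slope of 0.

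In both cases the loss of 48 is no longer visible.

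**Wider assumptions.** Take native eGFR falling from 40-90 to 10 over 5 to 16 years (true slope -5.0 to -6.25), followed by 2 to 10 years of later data. The whole-record slopes are:

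- graft from 30: -4.3 to -0.5
- graft from 50: -3.6 to +2.1
- graft from 60: -3.3 to +3.5
- dialysis at a constant 8: -5.6 to -1.8
- last value (10) carried forward: -5.5 to -1.6

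Every case is flatter than its native slope.

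**Group mean.** In an assumed group of 30, one patient from the first example moves the mean slope by (difference in slope)/30. With 8 later values, this is 6.4/30 = 0.21 per year (graft from 55) or 3.0/30 = 0.10 (carried). With 2 later values, it is 4.2/30 = 0.14 or 0.8/30 = 0.03.

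**The case against.** The strongest reply is that the reset may be only a descriptive device. The sentence follows the paragraph on change from the Analysis Start Date and precedes the analysis methods. The MMRM adjusts for enrollment eGFR, and a regression slope needs no baseline value. If the new baseline applies only after the event, change summaries before renal failure keep the native decline. A carried value in the MMRM is also doubtful, because 13.7 says that missing later measurements are not imputed and the protocol rules out imputation of missing data. These points stand. They mean that the effect on slopes and the MMRM comes mainly from the absence of truncation together with section 6.2, and that the reset acts on change from baseline. They do not supply a stop rule.

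Three stronger readings are tempting, and the documents do not support them:

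- **That the worst decliners become stable patients.** This depends on the graft and on how long it is followed. With two later values the slope is still -1.8 (graft from 55) or -5.2 (carried).
- **That all renal endpoints depart from the FACE rule.** Sections 13.8 and 13.9 inherit the exclusion, and renal FACEs follow the FACE sections.
- **That the comparison is tilted toward a particular treatment group.** No counts by group are given.

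It can also be said that ESRD is counted as a renal FACE, so these patients are not lost from view. That is only partly reassuring, because 13.1.1 also lists starting dialysis and kidney transplant among the reasons for censoring.

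**Conclusion.** The point holds for eGFR change, slope and MMRM in 13.7 and for creatinine in 15.6. As written, these analyses take in values recorded after dialysis or transplantation, unlike the FACE analyses and the endpoints that borrow their methods. Within an affected patient the bias was toward less decline in every case tried. It ranged from slight (-6.0 to -5.2 per year, value carried for two years) to complete (-6.0 to +0.4 per year, eight years of a graft starting at 55). The sizes rest on assumed trajectories and annual visits.

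The size and direction of any between-group bias are unknown. They depend on how many such patients each group has and on the spread of slopes, and the documents give neither. A shift of 0.03 to 0.21 per year in an assumed group of 30 therefore cannot be called large or small. The change should be made before analysis because it is cheap and settles an ambiguous rule for a tested secondary endpoint.

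**What to change.** Delete the reset sentence in SAP 13.7 and 15.6 and keep the original Analysis Start Date. Replace it with wording such as: *eGFR and creatinine values recorded after the start of dialysis or after kidney transplantation are excluded from slopes, the MMRM and change summaries, and are presented in listings only.* Define the events as in 13.1.1 to 13.3, which refer to starting dialysis without the qualifier long-term. Those sections also name heart transplant, so state whether it truncates the renal series too. Measured GFR in 16.8 is analysed by the methods of 15.6, so say that the rule covers it as well.

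The cost is SAP wording and the loss of a few later values from the models. Truncation also depends on outcome, because the record ends when the kidneys fail. Report the number of patients truncated by treatment group, and add a sensitivity analysis such as a joint model of eGFR and renal failure, or a composite of eGFR decline and ESRD. No new data collection is needed.
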